### 11.4 Frequency of data collection

Data will be collected immediately post-op, and every 4 hours thereafter, until 24 hours post-op, on the day of surgery.

### 11.5 Individual's reviewing the data

Oversight for the conduct of the study will be provided by the PI, and the research coordinator will monitor the data. They will ensure that all eligible criteria and consent requirements are met prior to a subject's participation in the study and that the procedures and adverse event reporting occur according to the IRB approved protocol.

### 11.6 Frequency of review of cumulative data

The PI and research coordinator will review cumulative adverse events, early termination of study participation, and accrual every six months and report any issues requiring modification of the study or alteration of the risk: benefit ratio to the IRB immediately. A summary of adverse events, study progress and protocol modifications will be included for IRB review in the continuing review.

### 11.7 Statistical tests

Not applicable.

### 11.8 Suspension of research

Not applicable.

## 12.0 Risks

Risks specific to this study include:

- Risk of randomization - patient will be assigned to a treatment program by chance. The treatment received may prove to be less effective than the other research treatment(s) or other available treatments.
- Loss of confidentiality associated with being part of a research study collecting personal health information.
- Ketamine adverse effects at proposed dosing include:
  - Uncommon: hypertension, increased cardiac output, increased intracranial pressure, tachycardia, tonic-clonic movements, visual hallucinations, vivid dreams, bradycardia,

diplopia, hypotension, increased intra-ocular pressure, injection-site pain, nystagmus, anaphylaxis, cardiac arrhythmia, depressed cough reflex, fasciculations, hyper salivation, increased metabolic rate, hypertonia, laryngospasm.

- Magnesium adverse effects at proposed dosing include:
  - Uncommon: flushing, drowsiness, circulatory collapse, respiratory paralysis, hypothermia, pulmonary edema, depressed reflexes, hypotension, depressed cardiac function, diaphoresis, hypocalcemia, hypophosphatemia, hyperkalemia, visual changes.
- Adverse effects related to the study medications at proposed dosing are uncommon. Most adverse effects noted were at higher dosing; there is limited literature noting adverse effects at proposed dosing.

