### **1.2 Primary Study Endpoints**

1. Total hydromorphone use in 1st 24 hours post-operatively.

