### **1.3 Secondary Study Endpoints**

1. Pain Scores using Visual Analogue Scale (VAS) [ Time Frame: 1st 24 hours post-op ]
2. Sedation scores using Ramsey Sedation Scale [ Time Frame: 1st 24 hours post-op ]
3. Nausea Scores using PONV Impact Scale Score [ Time Frame: 1st 24 hours post-op ] – see data collection sheet
4. Intraoperative fentanyl use [ Time Frame: Intraoperative period ]
5. Intraoperative minimum alveolar concentration (MAC) of desflurane
6. Sentec CO2 measurements, average PCO2 will be taken every hour [Time Frame: 1st 24 hours post-op].

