#### **7.2.5 Post- op**

As per standard of care, the patient will be taken to the post anesthesia care unit (PACU) and set up with standard ASA monitoring as well as the Sentec CO2 monitor which was applied in the SDU.. A hydromorphone patient controlled analgesia (PCA) pump will be set-up by nursing and given to the patient. Standard dosing of 0.2 mg bolus, every 6 minutes with a maximum 2 mg per hour will be the starting dose as is standard for these patients post-operatively. As per standard of care, 1 gm of Tylenol every 8hrs will also be scheduled to be administered via IV route for 1st 24hrs. If reported pain scores are beyond the patients previously determined acceptable pain score (asked pre-operatively per hospital standard) the PACU resident may give additional doses of IV hydromorphone at his/her discretion. When patient meets discharge criteria they will be sent from the PACU to their room with monitoring of continuous pulse oximetry and ETCO2 until 24 hours post-operation.

During the post-operative period, data will be recorded immediately upon arrival to PACU and every 4 hours thereafter with a maximum recording of 24 hours post-op. For study purposes, a data sheet will be assigned to the patient pre-operatively with pre-operative pain anxiety, and PONV scores recorded. The sheet will then be attached to the patients chart and data recorded by the nursing staff. At the end of the 24 hour period the sheets will be collected by one of the research team members.

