### 9.2 Statistical methods

Our current plan is to use ANOVA, along with pairwise comparisons, to compare the three groups with respect to pain scores (nonparametric ANOVA) and total hydromorphone use (parametric ANOVA) in the first 24 hours post-operatively, to determine whether there are any significant differences. We will use SAS, Version 9.4, for all statistical analyses.

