### 11.3 Method of collection of safety information

Safety information will be collected by the research staff preoperatively and post operatively as described in Section 7.2.

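### Hallucinations and vivid dreams are listed ketamine risks, but the plan describes no endpoint, prompted post-operative question or by-arm summary for them

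*Combined protocol and SAP*

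**What the plan says.** **Risk.** Section 12.0 puts "visual hallucinations, vivid dreams" and diplopia in its list of uncommon ketamine effects at the dosing used. It closes by saying that most adverse effects were seen at higher doses and that "there is limited literature noting adverse effects at proposed dosing".

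**Endpoints.** The primary endpoint (1.2) is 24-hour hydromorphone use. The six secondary endpoints (1.3) are VAS pain, sedation, the PONV impact scale, intraoperative fentanyl, desflurane MAC and Sentec CO2. The nearest to a central nervous system effect is "Sedation scores using Ramsey Sedation Scale".

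**Collection.** Section 11.3 states: "Safety information will be collected by the research staff preoperatively and post operatively as described in Section 7.2". In that section, 7.2.5 provides for recording at PACU arrival and every 4 hours up to 24 hours, on a sheet completed by nursing staff. The only contents it names are the baseline items: "pre-operative pain anxiety, and PONV scores recorded".

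**Analysis.** Section 9.2 plans ANOVA with pairwise comparisons "to compare the three groups with respect to pain scores (nonparametric ANOVA) and total hydromorphone use". Section 11.7, on statistical tests within safety monitoring, is marked not applicable.

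**General adverse-event route.** Section 21.2 follows events that come to the study team's notice and are thought to be drug-associated. Section 22.1.2 has them entered on adverse-event forms checked by the principal investigator. Sections 11.1 and 11.6 provide a cumulative review every six months. Section 21.5 sends the IRB only harms that are both unexpected and probably related.

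**The concern.** Sedation, nausea and CO2, where sparing opioid might be expected to help, are named endpoints. The subjective effects that the protocol itself attributes to ketamine are not, and the text describes no question that would bring them out. A hallucination or a vivid dream is known to staff only if the patient reports it.

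Section 13.1 presents fewer opiate side effects as a possible benefit, and 13.2 expects the results to inform pain protocols for obese patients across operations. That use needs both sides of the balance. If ketamine reduces hydromorphone use and few hallucinations or dreams are on file, a reader cannot tell whether they seldom occurred or were seldom mentioned.

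**Working it through.** **1. The plan's own sample size.** Section 9.1 cites a 48-hour mean of 52 mg with SD 22 mg. Halving for 24 hours gives 26 mg and SD 11 mg (halving the SD is inferred). A 25% reduction gives 26 × 0.75 = 19.5 mg, a difference of 6.5 mg. With one-sided alpha 0.05 and 80% power:

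n = 2 × (1.645 + 0.842)² × 11² / 6.5² = 35.4, so 36 per group.

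This matches the stated 36 per group and 108 in total (power 80.6%; a t-based calculation gives 37). The trial is sized on opioid use alone. The documents give no figure for any harm comparison.

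**2. Coverage of the two listed effects.**

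| Place | Covers hallucinations or vivid dreams? |
|---|---|
| 1.2, 1.3 endpoints | No; the nearest is a sedation score |
| 7.2.5 data sheet as described | No item described; the sheet itself is not shown |
| 9.2 analysis | No; pain and hydromorphone only |
| 21.2, 22.1.2 adverse-event forms | Yes, if noticed or volunteered |
| 11.1, 11.6 review | Cumulative; no comparison by arm described |
| 21.5 report to IRB | Generally no; an effect listed in the protocol is not unexpected under the 21.1 definition unless more specific or severe |

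**3. What a prompted item would give.** Ketamine patients: 2 × 36 = 72. With zero events, the exact two-sided 95% upper limit is

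- 72 patients: 1 − 0.025^(1/72) = 4.99%
- one arm of 36: 1 − 0.025^(1/36) = 9.7%

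The chance of at least one event among 72, 1 − (1 − p)^72, is 52%, 77% and 98% at assumed true rates of 1%, 2% and 5%.

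**4. What spontaneous report would give.** Let v be the share of affected patients who volunteer the effect. The documents do not give v. Zero reports among 72 bound the reported rate at 4.99%, so they bound the true rate at 4.99% / v. That is 5.0% if v = 100% and 4.99 / 0.30 = 16.6% if v = 30%, and it rises as v falls. In expected counts at an assumed true rate of 10%, 72 × 0.10 = 7.2 patients would be affected, and 7.2 × 0.30 = 2.2 would be recorded.

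**5. Could the trial test a difference?** Power of a two-sided 0.05 Fisher test, all rates assumed:

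| Ketamine vs control rate | 72 vs 36 | 36 vs 36 |
|---|---|---|
| 5% vs 1% | 2% | 1% |
| 10% vs 2% | 22% | 8% |
| 20% vs 2% | 78% | 56% |

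Only a large difference would be detected reliably, so the endpoint should be descriptive.

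**The case against.** The case for leaving the plan alone has several sound parts.

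- **Harm capture exists.** A reader might infer that the trial could report benefit with this harm wholly uncaptured. Sections 21.2, 22.1.2, 11.1 and 11.6 do not support that: a reported hallucination would be recorded and reviewed. What is missing is described prompting and a by-arm summary.
- **The literature sentence is reassurance.** A reader might take "there is limited literature noting adverse effects at proposed dosing" as an admission that evidence at this dose is sparse. In context it means that few adverse effects have been reported at this dose, and 2.3 describes both drugs as well studied. The point does not depend on that sentence.
- **The data sheet is unseen.** Silence in 7.2.5 does not prove that the question is not asked. That section does not list post-operative sedation scores either, although sedation is an endpoint. This stands, so the point concerns what is described. Even if the sheet has such an item, it is not an endpoint and has no planned summary.
- **Section 9.2 is thin in general.** It also omits sedation, nausea, fentanyl, MAC and CO2, so it does not single out this harm. True, but those measures are at least named as endpoints.
- **The effects are called uncommon, and schizophrenia and bipolar disorder are excluded (3.2).** Both lower the expected count. Neither replaces asking.
- **The trial is too small.** For a test this is right, as step 5 shows. It is no argument against counts with intervals.

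**Conclusion.** The point holds as a cheap improvement, not as a defect that threatens the primary result. As described, the plan leaves two listed, subjective ketamine effects to spontaneous report, with no endpoint and no by-arm summary, although 72 of 108 planned completers receive the drug.

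The size of the gain is the difference between an upper limit of 5.0% after zero prompted events in 72 and a limit of 4.99% / v after zero spontaneous reports. A reader might infer that unprompted zeros support no bound at all. That goes too far: they support a weaker one, about 17% at v = 30%, which depends on a volunteering share that the trial would not measure. The 30% share and all event rates above are assumptions. The 5.0% figure also assumes that patients answer the prompted question accurately. The conclusion on coverage rests only on the text, with the data sheet unseen.

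**What to change.** 1. **Section 1.3:** add a descriptive secondary safety endpoint, any hallucination or any vivid or unpleasant dream in the first 24 hours.
2. **Section 7.2.5:** unless the data sheet already has it, add one yes/no item at PACU arrival and at each 4-hourly check. Name who asks, because 11.3 refers to research staff and 7.2.5 to nursing staff. State that they are blinded: 7.2.2 and 7.4.3 name the patient, the anesthesia team and the research team, but not the nurses.
3. **Section 9.2:** report the number of patients with any event in each of the three arms with exact 95% intervals, and the risk difference of each ketamine arm against control with its interval. Plan no powered test.
4. **Double vision:** report it separately. Section 12.0 lists visual changes for magnesium too, so including it in the composite could credit a magnesium effect to ketamine.
5. **Sections 21.6 and 21.7:** state how a yes answer relates to the unblinding and stopping text. Section 21.6 unblinds for a possible reaction, 7.2.2 for a concerning one, 21.7 then stops the study protocol, and 11.8 marks suspension as not applicable. These passages must be reconciled; which rule should apply is for the investigators. If every yes led to unblinding, later pain scores could be unblinded more often in the ketamine arms.

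**Cost:** one line on an existing form, at most seven answers per patient (arrival plus 24 / 4 = 6 checks), and one table, with no extra visit. Prompting will raise reported rates somewhat. The control arm shows the background level, but an equal rise in every arm depends on the blind holding.

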## 13.0 Potential Benefits to Subjects and Others

### 13.1 Potential Benefits to Subjects

Potential benefits of being a subject in the study include improved pain control, less nausea/vomiting, less sedation, fewer side effects from opiates, and decreased length of hospital stay.

### 13.2 Potential Benefits to Others

This study will provide data that may potentially create improved pain management protocols in obese patients undergoing general anesthesia for any operation.

## 14.0 Sharing Results with Subjects

N/A – results of the study will have no impact on clinical care already received by the patients and many of the subjects may be lost to follow-up.

## 15.0 Economic Burden to Subjects

### 15.1 Costs

There will be no costs to the subject associated with their participation in the study other than those associated with normal standard of care medical care utilization. The study drug, ketamine and/or magnesium will be provided by Hershey Medical Center.

### 15.2 Compensation for research-related injury

It is the policy of the institution to provide neither financial compensation nor free medical treatment for research-related injury. In the event of injury resulting from this research, medical treatment is available but will be provided at the usual charge. Costs for the treatment of research-related injuries will be charged to subjects or their insurance carriers.

## 16.0 Number of Subjects

See Section 9.

## 17.0 Resources Available

### 17.1 Facilities and locations

This study will be completed at Penn State Hershey Medical Center. This is a large university based tertiary care center where gastric sleeves are frequently completed.

### 17.2 Feasibility of recruiting the required number of subjects

The required number of patients (see Section 9) needed should be attainable in 8-10 months according to current numbers being operated on at Hershey Medical Center. The project will continue until this number is obtained. The access to these patients will not be limited by the surgical team.

**17.3 PI Time devoted to conducting the research**

The PI has completed multiple research projects previously and has significant experience as well as appropriate RTA time.

**17.4 Availability of medical or psychological resources**

All resources needed for the protocol, as well as for any possible adverse event, are available at Penn State Hershey Medical Center.

**17.5 Process for informing Study Team**

Meetings will be held periodically as needed to ensure all research team members are informed about the protocol and their duties. Team emails will also be used to keep team members updated.

## **18.0 Other Approvals**

Departmental Scientific Review

## **19.0 Subject Stipend (Compensation) and/or Travel Reimbursements**

Not applicable.

## **20.0 Multi-Site Research**

Not applicable.

## **21.0 Adverse Event Reporting**

**21.1 Adverse Event Definitions**

For drug studies, incorporate the following definitions into the below responses, as written:	
Adverse event	Any untoward medical occurrence associated with the use of the drug in humans, whether or not considered drug related
Adverse reaction	Any adverse event caused by a drug
Suspected adverse reaction	Any adverse event for which there is a reasonable possibility that the drug caused the adverse event. Suspected adverse reaction implies a lesser degree of certainty about causality than "adverse reaction". 

Reasonable possibility. For the purpose of IND safety reporting, "reasonable possibility" means there is evidence to suggest a causal relationship between the drug and the adverse event.

Serious adverse event or Serious suspected adverse reaction	Serious adverse event or Serious suspected adverse reaction: An adverse event or suspected adverse reaction that in the view of either the investigator or sponsor, it results in any of the following outcomes: Death, a life-threatening adverse event, inpatient hospitalization or prolongation of existing hospitalization, a persistent or significant incapacity or substantial disruption of the ability to conduct normal life functions, or a congenital anomaly/birth defect. Important medical events that may not result in death, be life-threatening, or require hospitalization may be considered serious when, based upon appropriate medical judgment, they may jeopardize the patient or subject and may require medical or surgical intervention to prevent one of the outcomes listed in this definition.
Life-threatening adverse event or life-threatening suspected adverse reaction	An adverse event or suspected adverse reaction is considered "life-threatening" if, in the view of either the Investigator (i.e., the study site principal investigator) or Sponsor, its occurrence places the patient or research subject at immediate risk of death. It does not include an adverse event or suspected adverse reaction that had it occurred in a more severe form, might have caused death.
Unexpected	An adverse event or suspected adverse reaction is considered "unexpected" if it is

adverse event or Unexpected suspected adverse reaction.	not listed in the investigator brochure, general investigational plan, clinical protocol, or elsewhere in the current IND application; or is not listed at the specificity or severity that has been previously observed and/or specified.
--	--

## 21.2 Recording of Adverse Events

All adverse events (serious or non-serious) and abnormal test findings observed or reported to the study team believed to be associated with the study drug(s) or device(s) will be followed until the event (or its sequelae) or the abnormal test finding resolves or stabilizes at a level acceptable to the investigator.

An abnormal test finding will be classified as an adverse event if one or more of the following criteria are met:

- The test finding is accompanied by clinical symptoms
- The test finding necessitates additional diagnostic evaluation(s) or medical/surgical intervention, including significant additional concomitant drug treatment or other therapy.  
**Note:** Simply repeating a test finding, in the absence of any of the other listed criteria, does not constitute an adverse event.
- The test finding leads to a change in study drug dosing or discontinuation of subject participation in the clinical research study.
- The test finding is considered an adverse event by the investigator.

## 21.3 Causality and Severity Assessments

The investigator will promptly review documented adverse events and abnormal test findings to determine 1) if the abnormal test finding should be classified as an adverse event; 2) if there is a reasonable possibility that the adverse event was caused by the study drug(s) or device(s); and 3) if the adverse event meets the criteria for a serious adverse event.

If the investigator's final determination of causality is "unknown and of questionable relationship to the study drug(s) or device(s)", the adverse event will be classified as associated with the use of the study drug(s) or device(s) for reporting purposes. If the investigator's final determination of causality is "unknown but not related to the study drug(s) or device(s)", this determination and the rationale for the determination will be documented in the respective subject's case history.

## 21.4 Reporting of Adverse Reactions and Unanticipated Problems to the FDA

Not applicable

## 21.5 Reporting Adverse Reactions and Unanticipated Problems to the Responsible IRB

In accordance with applicable policies of The Pennsylvania State University Institutional Review Board (IRB), the investigator will report, to the IRB, any observed or reported harm (adverse event) experienced by a subject or other individual, which in the opinion of the investigator is determined to be (1) unexpected; and (2) probably related to the research procedures. Harms (adverse events) will be submitted to the IRB in accordance with the IRB policies and procedures.

## 21.6 Unblinding Procedures

In the event a patient becomes unstable for any reason, or has a possible reaction to a study medication as determined by the primary anesthetic provider, the patient will immediately be unblinded from the study.

## 21.7 Stopping Rules

In the event of a reaction requiring unblinding, the study protocol will be stopped.

## 22.0 Study Monitoring, Auditing and Inspecting

### 22.1 Study Monitoring Plan

#### 22.1.1 Quality Assurance and Quality Control

This is a low risk therapeutic study using agents with a known safety profile. The PI will ensure that this study is conducted, and that the data are generated, documented (recorded), and reported, in compliance with this protocol, with institutional and IRB policies, with Good Clinical Practice guidelines and any other applicable regulatory requirements.

#### 22.1.2 Safety Monitoring

The **Principal Investigator** will confirm that all adverse events (AE) are correctly entered into the AE case report forms by the coordinator; be available to answer any questions that the coordinators may have concerning AEs; and will notify the IRB, FDA, sponsor and/or DSMB of all applicable AEs as appropriate. All assessments of AEs will be made by a licensed medical professional who is an investigator on the research.

The **research coordinator** will complete the appropriate report forms and logs; assist the PI to prepare reports and notify the IRB, FDA, and/or DSMB of all Unanticipated Problems/SAE's.

## 24.0 Appendix
